Power Calculations. Statistical power for Aim 1 was computed across a range of plausible effect sizes and outcome prevalence estimates. Power was estimated conservatively, assuming that of the 800 total participants and their network members, 10% would meet the current CDC recommended criteria for testing (recent exposure, symptoms, or congregate housing) and thus the sample size for the primary testing outcome was estimated at N=80 eligible participants. We assumed that 30% would previously have been fully vaccinated or infected with COVID-19 in the past 6 months, resulting in an analytic sample size for vaccination outcomes of N=560 participants and their network members. Power may change depending on the evolution of the pandemic (e.g., changes in infection rates, prevalence of variants, and/or local public health guidance regarding testing and booster vaccine recommendations), and will be higher with broader testing eligibility, higher outcome prevalence, and for analyses treating each network member as a separate observation. For each outcome, we computed minimum detectable effect sizes given estimated rates of testing and vaccination in the control group. We estimated 3-month testing rates among those eligible for testing of 10% in the control group. Based on our ongoing influenza vaccination work, as a starting point for calculations we estimated 3-month vaccination rates among study participants and their network members of approximately 30%. All calculations were conducted in Stata/SE version 15.1 with alpha=0.05, two-sided tests, and a 2:1 ratio of randomization to the intervention vs. control group. For participant testing (primary outcome 1), with a sample size of 80 eligible participants and control group testing prevalence of 10%, we would have 80% power to detect differences of 28 percentage points or more (proportion tested in the intervention group $\geq 38\%$). For participant vaccination (primary outcome 2), with a sample size of 560 and vaccination prevalence of 30% in the control group, we would have 80% power to detect differences of ≥ 12 percentage points (proportion vaccinated in the intervention group $\geq 42\%$). For evaluating interaction effects (Aim 1b), with a sample size of 560 we would have $>80\%$ power to detect an interaction between intervention assignment and an evenly distributed binary covariate (50% in group A and 50% in group B) when vaccination prevalence in the control group is 30% and the intervention increases vaccination to 40% in group A and 69% in group B (e.g., the intervention is more effective in group B). For the participant testing outcome, we will have limited power to detect interaction effects except those of very large magnitude, but will explore differences in testing across

subgroups to guide future work. For the network outcomes (secondary outcome 1&2), we assume that the number of network members tested/vaccinated follows a negative binomial distribution with an over dispersion parameter equal to 2 to reflect variability among participants in terms of testing and vaccination referrals. For network testing, with a sample size of 800 participants (with an average of 2-3 named network members per participant), we would have $\geq 80\%$ power to test the null hypothesis of no difference between groups if the mean number of tested network members per participant is 0.12 in the control group and 0.25 in the intervention group (i.e., the intervention increases the proportion of participants with any network members tested from 10% to 18% and the proportion with >2 network members tested from 0.2% to 1.3%). For network vaccination, with a sample size of 560, we would have $>80\%$ power to test the null hypothesis of no difference between groups if the mean number of vaccinated network members per participant is 0.51 in the control and 0.92 in the intervention group, which reflects a scenario where the intervention increases the proportion of participants with any network members vaccinated from 30% to 41% and the proportion with more than 2 network members vaccinated from 5.1% to 12.1%. Thus, we will have sufficient power to detect effect sizes consistent with our previous work.

Attrition and missing data. All participants enrolled in the study will be included in our analyses; since the primary outcome will be measured based on testing/vaccine registry data we are confident that there will be limited missing data given that this type of registry has considerable resources to support it and is required for the EUA status. As an additional precaution, all participants will be interviewed to assess for testing/vaccination status among themselves and network members at 3 months. Thus, we anticipate very little missing outcome data. Any missing data will be addressed using multiple imputation⁷⁴ or by using a fully Bayesian approach to estimate the model⁷⁵ (in which missing data are essentially treated as additional unknown parameters).

POTENTIAL RISKS AND BENEFITS TO SUBJECTS

In general, protection against risk to participants will be accomplished through thorough training of research staff; careful orientation of potential participants as to the nature, risk, and benefits of the research; strict adherence to study protocols; and regular surveillance for adverse events. Additionally, this study will receive an NIH Certificate of Confidentiality to further protect information shared.

- The following steps will be taken to protect the confidentiality of all data generated and collected throughout the course of the study:
- Data access will be limited to a specified group of programmers and researchers identified as study personnel. An audit trail will be maintained to track all user-access to the data.
- All study investigators and research team personnel will be trained in the importance of confidentiality and trained to follow all rules related to handling confidential data.
- All data sets resulting from this study will be kept exclusively in the BSD CRI system at the University of Chicago, access to which requires administrative approval and password. The internal server is encrypted at the storage, backup, and sharing levels, thereby maximizing protections against breaches of confidentiality.
- The research team will not be permitted to copy the raw data or to transmit the raw data other than through a secure server connection.
- Results of the study will be reported only in the aggregate and without other identifiable data, with attention to issues of statistical disclosure.

Protection of privacy. All study procedures will be performed in quiet, private spaces to ensure confidentiality. If covid test results and/or vaccine status is communicated via email or text picture using a cell phone, this communication would occur with the subject's site study personnel only. The testing/vaccination data would be recorded and the email/text picture would be deleted. The images

are not retained or shared.

Protection against psychological discomfort. Survey questions may touch on potentially sensitive topics. Participants will be informed of this possibility through assent/consent procedures and they will be reminded that they may skip questions or discontinue participation altogether. If a participant expresses distress directly to the research team, they will be provided the name and contact information of several licensed behavioral health providers on our research team and other local resources as needed.

Protection against testing risks. Testing Procedures and Infection Control Measures. All COVID-19 testing procedures will take place according to SOPs at each of the participating partnering health departments and clinics. These procedures ensure that appropriate infection control measures, a COVID-19 screener (Appendix C), counseling, including quarantine and isolation procedures, masking and results disclosures are provided in accordance to the current standard of care and CDC guidelines. Monetary, food, other tangible supports, and/or linkage to further medical evaluation and will be provided for individuals who test positive and require resources to adhere to quarantine and social distancing requirements. Performance of surveys and interviews will abide by social distancing guidelines.

Benefits: The potential benefits of this research far outweighs the risks. For individual participants, benefits include COVID-19 testing/vaccination information and reduced likelihood of COVID-19 severe complications and hospitalizations, with provision of financial and other tangible resources for quarantine and isolation as well as linkage to medical care if necessary. Possible risks (i.e. discomfort answering questions, potential confidentiality breaches, stigma) are outweighed by the new knowledge gained as described above and the direct clinical benefits and supportive services to participants.

DATA STORAGE AND SHARING

We will take several steps to ensure the security of the identifiers and data collected for this study. All data will be collected using dedicated laptops purchased by the project and configured and certified by BSDIS to meet their requirements for portable computers (e.g., timed log-out, whole-disk encryption, use of BigFix and antivirus software, etc.). Data will be entered into REDCap (web-based application hosted by the CRI at the University of Chicago). This data will be maintained on a HIPAA compliant, secure server hosted at the University of Chicago.

The identifiers of social network members (first name and last initial only) will be uploaded and stored in a separate, dedicated file share held on a secure, HIPAA compliant server at the University of Chicago, accessible only by the data analyst team who will be located at the University of Chicago and NORC. Social network identifiers will not be shared outside of the data analyst team and will not be accessible to the wider study team. The data analyst team will monitor the incoming files to ensure confidentiality. Social network identifiers are used to analyze whether the study interventions affect the study subject and their social network members' likelihood of becoming vaccinated and/or testing for COVID (based on the study subject's survey response). Once this analysis has been completed, all files containing network member identifiers will be destroyed.

Upon study termination, participant identifiers will be removed from the study dataset. All recordings of study trainings will be destroyed upon study termination. The de-identified study data may be maintained indefinitely at the University of Chicago.

UAMS will destroy any raw data received from Arkansas Department of Health upon study completion.

Data Transfer:

Before any data transfer, the University of Chicago will encrypt the data both at rest and in transit to provide a high level of security of sending and receiving file transfers. The encrypted data products will be securely uploaded to a server using a cyberinfrastructure service such as Globus (<https://www.globus.org/>) via the Biological Science Division Information Services (BSDIS). This will ensure high security features that meet authentication and authorization standards for sensitive data containing protected health information. Additionally, data management and transferring services for personally identifiable data will be with a High Assurance or HIPAA BAA subscription. If an institution is responsible to provide data (incoming), they will be responsible for encryption.

Northwestern University

Northwestern (NWU) will assist with data analysis for the planned qualitative interviews and survey data. NWU will receive text transcripts from interviews as well as survey data for analysis. These data may contain dates and zip codes but will not contain any other identifying information (such as names). Shared data will be linked to the subject's unique ID number, but the key will be kept by the University of Chicago team and not shared.

NIH and DCRI

The Duke Clinical Research Institute (DCRI) has been chosen by the National Institute of Health (NIH) to serve as the data coordinating center for all of the RADx-UP study centers (note, outside of our multi-center studies, there are other institutions who have received funding from the NIH to conduct related research under the RADx funding initiative). A limited study data set (includes zip codes and dates) will be shared with DCRI to link area level data sets and to add context to the socioeconomic, environmental, and public health outcomes in larger data sets. DCRI will maintain a database that can be shared with RADx-UP consortium members (those who are conducting the RADx-UP studies) for future research. The consortium database will include zip codes and dates and will be maintained by DCRI indefinitely. RADx-UP consortium members will be required to apply to use this dataset. All data shared for future research in this manner would be de-identified and could be used indefinitely.

DCRI will also transfer a de-identified study data set to the NIH for purposes for future research in keeping with the NIH's policy. All data shared for future research in this manner would be de-identified and could be used indefinitely.

REFERENCES:

3. [name] JA, Young L, Ramachandran A, et al. A Pragmatic Randomized Controlled Trial to Increase PrEP Uptake for HIV Prevention: 55-Week Results From PrEPChicago. *J Acquir Immune Defic Syndr.* 2021;86(1):31-37. doi:10.1097/QAI.0000000000002518

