- (4) previous direct or indirect exposure to law enforcement
- (5) has covid vaccination and applicable boosters (self-report, not required to show proof)

Exclusion Criteria:

- (1) inability to provide informed consent; and
- (2) active COVID-19 symptoms per CDC.⁵⁶

(3) Parolees currently living in a court ordered treatment center as part of parole and/or individuals otherwise meeting the definition of a prisoner

We include participants with prior COVID-19 vaccination (completed series) or recent COVID-19 infection in past 3 months given that they may be important change agents. We will remove the estimated numbers (n=160) who are vaccinated/recent infection from our primary analysis if there are no future vaccine boosters or new vaccines required (i.e., new variant). Candidate participants with COVID-19 symptoms will be referred for free testing at existing partners for each of the study sites.

Sex as a Biologic Variable. Both sexes and all genders will be included in this study with exploratory analyses to determine any differences in intervention effects.

STUDY VISIT PROCEDURES

[figure not shown]
Study procedures include:

- 1) Informed consent, locator form
- 2) Baseline survey with network elicitation
- 3) Randomization
- 4) Motivational or Education intervention (approximately 3 hours)
- 5) Booster/Communication 30-day \pm 7 days phone follow-up
- 6) 3-month follow-up phone survey \pm 7 days to assess participant and network COVID-19 testing/vaccination history

Eligible candidate study participants will undergo written informed consent. Following consent, study participants will complete a survey (Baseline Assessment) includes variables of interest and the social network inventory. Randomization will occur following the survey, and participants will be assigned to one of two concurrent Motivational or Educational group-level sessions. Sessions will be held weekly, also with availability, in the evening or on weekends. Study staff will be notified of group allocation and bring study participants to the appropriate group session/intervention rooms.

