Primary Outcomes. Two primary outcomes will be assessed at the level of the participant: the probability of receiving at least one 1) test and 2) vaccination dose within 3 months of baseline. Outcomes will be ascertained specifically by testing/vaccine registry data held by city and state held vaccine registries (Letters, [name], [name], [name]). Study participants will sign release of information forms, as in RADx-UP Phase I, in order for study staff to obtain 3-month testing/vaccination disposition statuses. Covid testing/vaccination status may also be provided by subject showing a copy of their covid testing result and/or vaccination information. This may be provided in person, shown during a video call, emailed or texted as a picture. Finally, study staff will reach out to all study participants (N=800) at 3 months following baseline to collect information on testing and vaccination uptake among study participants and barriers and facilitators for both network members and study participants. During

this assessment, information on situation appropriate testing will be collected to better understand the circumstances and context of testing. At the time of this writing, situation appropriate testing includes testing if symptomatic, if exposed to someone with COVID-19 infection and if entering a congregate living setting. Only participants reporting symptoms, exposure, and/or congregate housing will be included in the primary testing outcome analysis; post-hoc analysis will include all participants tested irrespective of the situation/context.

Secondary Outcome. Two secondary outcomes will be assessed at the level of the secondary subjects (network member connected to primary participant): the probability of receiving at least one 1) test and 2) vaccination dose within 3 months of baseline. Network member information, including identifying information will be collected during the baseline assessment through specialized network canvas software (described above). The secondary outcome will be determined based upon self-report from participants during the 30 and 90-day follow-up surveys. Note that this information is collected based asking the study subject whether the social network contact underwent these activities and not from contact with or medical record data collection of the social network member. Analyses for our secondary outcome will account for variability in network size across individuals.

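### Inclusion criterion (5) requires every enrollee to be vaccinated, which conflicts with the n=160, N=560 and all-enrolled statements on who is eligible and who is analysed for primary outcome 2

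*Combined protocol and SAP*

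**What the plan says.** **Eligibility.** Under Inclusion and Exclusion Criteria, numbered inclusion item (5) reads "has covid vaccination and applicable boosters (self-report, not required to show proof". It carries no exception. The words in parentheses say how the status is ascertained; they do not make it optional.

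**Subgroup and removal rule.** The paragraph after the exclusion list says "We include participants with prior COVID-19 vaccination (completed series) or recent COVID-19 infection in past 3 months", because such people may be useful change agents. It then says the team will "remove the estimated numbers (n=160) who are vaccinated/recent infection from our primary analysis if there are no future vaccine boosters or new vaccines required".

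**Power Calculations.** The section takes a different share and a different infection window from that paragraph: "We assumed that 30% would previously have been fully vaccinated or infected with COVID-19 in the past 6 months". It bases the vaccination outcome on the other 70%, that is, on 560 of the 800. The control rate is introduced with "Based on our ongoing influenza vaccination work, as a starting point for calculations we estimated 3-month vaccination rates" and set at about 30%. The stated result is 80% power for a difference of 12 points (30% against 42%).

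**Primary Outcomes.** The two outcomes are "assessed at the level of the participant: the probability of receiving at least one 1) test and 2) vaccination dose within 3 months". Vaccination status at entry is not mentioned.

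**Attrition and missing data.** Every enrolled participant is to be included in the analyses, with no booster condition.

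**Randomization.** Allocation is 1:1, stratified by site and by characteristics such as prior infection or vaccination.

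**The concern.** A status required of all enrollees cannot also be expected in only 20% or 30% of them. Staff who screen from the numbered list would turn away the unvaccinated people from whom the 560 are to be drawn. Staff who follow the later paragraph would enrol them. The two practices recruit different populations for one of the two primary outcomes.

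The analysis set is also inconsistently defined. One section removes a subgroup depending on later booster policy, another removes a different share outright, and a third removes nobody. No time is given for deciding whether the booster condition is met, so the choice could be made after outcome data are available.

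If criterion (5) is meant, the outcome counts a further dose among people who report being up to date. A 30% control rate taken as a starting point from influenza vaccination work is not tied to that population.

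**Working it through.** **1. The plan's own figure.**

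- Inputs from Power Calculations: N = 560, control 30%, intervention 42%, two-sided alpha 0.05, 80% power, 2:1 allocation.
- 800 × (1 − 0.30) = 560, as stated.
- Power = Φ[(d − 1.96·s0)/s1], where d is the difference, s0 = √[p̄(1 − p̄)(1/n1 + 1/n2)] and s1 = √[p1(1 − p1)/n1 + p2(1 − p2)/n2].
- With n1 = 186.7 and n2 = 373.3: p̄ = 0.38, s0 = 0.0435, s1 = 0.0422.
- Power = Φ[(0.12 − 0.0853)/0.0422] = 0.795. The difference detectable at 80% power is 12.08 points. The plan's figure reproduces on its own inputs.

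**2. Share of the 800 expected to be vaccinated or recently infected.**

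| Source | Share | Infection window |
|---|---|---|
| Criterion (5) as written | 800 of 800 (all vaccinated) | none stated |
| Paragraph after the exclusions | 160/800 = 20% | 3 months |
| Power Calculations | 0.30 × 800 = 240 (30%) | 6 months |

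The 160 and 240 combine vaccinated with recently infected people, so they do not count the vaccinated alone. Both are still far below 800.

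**3. Analysis set for primary outcome 2, by the statement followed.**

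| Statement followed | Set |
|---|---|
| Power Calculations | 800 − 240 = 560 |
| Removal rule, n=160, no new booster or vaccine required | 800 − 160 = 640 |
| Removal rule not triggered, or Attrition and missing data | 800 |
| Limiting case: criterion (5) literal, removal rule applied, no new booster or vaccine required | 800 − 800 = 0 |

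**4. Whether power suffers.** The same formula at the design's 1:1 allocation, holding the control rate at 30%:

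| N | Detectable difference | Power for 30% against 42% |
|---|---|---|
| 560 | 11.32 points | 0.843 |
| 640 | 10.56 points | 0.887 |
| 800 | 9.42 points | 0.944 |

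The move from 12.08 to 11.32 at N=560 comes only from 2:1 against 1:1 allocation, which is a separate inconsistency. The table shows only that no non-empty set is worse than planned while 30% holds.

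**5. A further sign of the conflict.** If criterion (5) is literal, the vaccination part of the stratification factor is constant. The infection part still varies.

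**The case against.** The strongest reply is that the intent is plain: the later paragraph gives a reason for admitting vaccinated people, and stratifying on vaccination presumes that the status varies. On that view criterion (5) is a drafting slip for a permission. This is plausible, but the numbered list still states a requirement, and the documents do not say which statement governs. A reader might infer that the plan is silent on required against permitted. It is not silent: the list says one and the paragraph says the other.

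The plan also warns that "Power may change depending on the evolution of the pandemic", and names booster recommendations among the causes. That covers changing circumstances. It does not say who is eligible or who is removed.

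A reader might infer that nobody is left to analyse. That needs three things together: criterion (5) taken literally, no new booster or vaccine required, and the removal rule applied despite the all-enrolled statement. It is a limiting case, not the expected result.

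A reader might also infer that the outcome must be redefined. It need not be. At least one dose within 3 months applies to vaccinated and unvaccinated people alike; only the planning figures are tied to a population.

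Finally, a partly vaccinated person might report meeting criterion (5). The statement that the 560 would be turned away therefore assumes that people who are not fully vaccinated fail it. That limit stands.

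**Conclusion.** The contradiction is in the current text and must be resolved. Criterion (5), the subgroup paragraph, Power Calculations and the all-enrolled statement disagree on eligibility and on the analysis set for primary outcome 2, which is 560, 640 or 800 depending on the section followed. If criterion (5) is applied as written, the 560 cannot be enrolled, assuming that people not fully vaccinated fail it, and the 30% control rate has no stated link to those who are enrolled.

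A reader might infer that the trial is underpowered. The documents do not support that: at a 30% control rate and 1:1, every non-empty set detects less than 12 points. Nor do they show adequate power if vaccination is required, because they give no control rate for a further dose.

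**What to change.** The sponsor should reconcile criterion (5) with the paragraph after the exclusions and with Randomization, Power Calculations, and Attrition and missing data, and state whether prior vaccination is required or only permitted and recorded.

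- **If only permitted:** take it off the inclusion list and keep it as a recorded baseline status.
- **If required:** keep the outcome as defined, and replace N=560, 30% and 12 points with figures for that population at 1:1.
- **In either case:** define one vaccination analysis set before outcome data are seen, with one removal share and one infection window (20% and 3 months now stand against 30% and 6 months) and a stated time for the booster decision. Bring the all-enrolled statement into line with it.

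The cost is a wording amendment through both IRBs (University of Chicago and Indiana University) and, if vaccination is required, a recomputed power statement. The documents do not give enrolment status, so any effect on people already screened is unknown.
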